The conduct of this visit may be altered to ensure patient safety during the global COVID-19 pandemic. If permitted and approved by regional regulatory authorities and the appropriate IRB/IEC, this visit may be converted to a remote visit (telephone, telemedicine, etc.) or conducted within the patient's home by a qualified visiting nurse. After obtaining either written or verbal consent from the patient, verifying the correct shipping address and patient availability to receive the shipment, IMP dispensation may be completed by utilizing an appropriate courier service. IMP may also be dispensed utilizing curbside pick-up at the site by the patient or patient representative. The procedures and data collected will be dependent upon the type of visit that is conducted. However, at a minimum, it is expected that the following data be collected regardless of whether the visits is conducted by phone or by visiting nurse: concomitant medications, assessment of AEs, SAEs, and clinical endpoints, and IMP adherence. When visits are conducted in the patient's home by a qualified visiting nurse, it is also expected, if logistically possible, that weight, vital signs, and samples for central laboratory evaluations will also be collected. Alterations to study visits and procedures during the pandemic will be recorded on a COVID-19-specific case report form.

Local laboratories may be utilized during the pandemic at the investigator's discretion with the following requirements:

- Lipids should not be assessed by local laboratories during the study. However, if lipids are included in a local laboratory report, care must be taken to ensure that the values remain masked for study site personnel, the patient, CRO, and Sponsor.
- A copy of the lab results and reference ranges, with lipid results redacted, must be filed within the patient records.

In individual cases after the pandemic has been determined to be over and if permitted and approved by regional regulatory authorities and the appropriate IRB/IEC, these visits may continue to be conducted within the patient's home by a qualified visiting nurse. In instances

where it is identified as necessary, IMP dispensation may be completed utilizing either an appropriate courier service (after obtaining consent and verification of shipping address and patient availability) or curbside pick-up at the site.

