16.1.2. Adverse Events of Special Interest

 AESIs will be identified by specified MedDRA PTs, or the related laboratory criteria if applicable. See [Appendix 7](#) for the list of AESIs and their definitions. These events will be summarized by AESI category, laboratory criteria met (if applicable), and PTs.

The NODM AESI is applicable only for patients with baseline glycemic status ([Section 7.4](#)) of No Diabetes at baseline. As an AESI vs. an efficacy endpoint, NODM includes a broader definition of NODM with patients who meet one of the following conditions:

- patients with verified NODM as determined by the DC ([Section 7.4.3](#)), or
- patients who initiated a diabetes medication after first dose of IMP ([Appendix 8](#)), or
- patients meeting the laboratory criteria for NODM as in [Appendix 7](#), or
- patients with selected AE preferred terms (see list of preferred terms for ‘NODM’ in [Appendix 7](#)).

Worsening Hyperglycemia AESI is applicable to patients with baseline glycemic status of Diabetes based on adverse event preferred terms as described in [Appendix 7](#).

See [Appendix 7](#) for the list of AESIs and their definitions. AESIs will be identified by specified MedDRA PTs, and/or the related laboratory criteria if applicable. These events will be summarized by treatment group, and by AESI category, laboratory criteria met, and PTs.

Malignancy AESI will be summarized by Standardised MedDRA Queries (SMQs) and PTs as described in [Appendix 7](#).

Tendon rupture will be summarized for events that are positively adjudicated according to the TRAC Charter. All potential tendon ruptures that were reviewed by the TRAC will be presented in a listing.

For AEs considered to be muscle related by the Investigator, additional information is collected on the *Muscle Related Adverse Event Complementary* CRF including the primary cause, locations, and whether the AE is unilateral or bilateral.

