16.3. Safety Laboratory Evaluations

The list of central laboratory assessments to be included in the outputs is included in the Table 4 of the Protocol (Section 12.1.6.1) and includes H_bA_{1c}. Urinalysis is not quantitative, and coagulation is measured at selected patients/visits only, and these will not be summarized.

In addition, eGFR will be calculated using the formula: $186 \times (\text{creatinine}/88.4)^{-1.154} \times (\text{age})^{-0.203} \times (0.742 \text{ if female}) \times (1.210 \text{ if Black})$, where creatinine is in μmol/L. Blood urea nitrogen (BUN)/creatinine ratio (BUN/Creatinine ratio) will also be calculated.

Summaries for all lab results will be included for the below analyses:

- Observed and change/percent change from baseline by analysis visit for hematology and blood chemistry measurements.
- Creatinine and eGFR will be summarized by treatment group and by baseline eGFR categories (<30, 30 to <60, 60 to <90, and ≥90 mL/min/1.73m²).
- Fasting glucose and HbA_{1c} will be summarized by baseline glycemic status, and by treatment group.

[figure not shown]
The analyses for shift tables from baseline to the worst post-baseline category or value are presented in Table 2. Note that for fasting glucose and HbA_{1c} the analyses will be by baseline glycemic status.

Table 2: Analyses for Shift Tables of Laboratory Parameters

Parameter	Categories (From Better to Worse)
Fasting glucose (by baseline glycemic status)	<51 mg/dL ≥51 to <100 mg/dL ≥100 to <126 mg/dL ≥126 mg/dL
H _b A _{1c} (by baseline glycemic status)	<5.7% ≥5.7% and <6.5% ≥6.5 to <7% ≥7%
Alanine aminotransferase (ALT)	Normal, High (> ULN)
Aspartate aminotransferase (AST)	Normal, High (> ULN)
eGFR	≥90 mL/min/1.73m ² ≥60 to <90 mL/min/1.73m ² ≥30 to <60 mL/min/1.73m ² <30 mL/min/1.73m ²
Uric acid (UA)	Low/Normal (combined) High (> 5.7 mg/dL for female, >7.0 mg/dL for male)

Lab abnormalities associated with AESIs are listed in Appendix 7 and will be summarized with the AESIs. In addition, for evaluation of potential Hy’s Law cases, a pairwise scatterplot will be created with the maximum (peak) post-baseline values of ALT or AST as multiples of the ULN, against the concomitant TB (also multiples of the ULN).

Other lab abnormalities of selected parameters are presented in Table 3 and the number of patients meeting each criterion will be summarized by treatment group.

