Patients with potentially clinically significant laboratory abnormalities (Appendix 10) will be listed. For a given parameter (or group of parameters as indicated), all values from the patient will be included in the listing if any value meets the criteria.

As a result of the pandemic, local laboratory may be used for safety labs at the investigators’ discretion. The local lab data are reviewed and evaluated by the investigators for any abnormalities and adverse event reporting as applicable. Due to the diverse use of units and

variation in laboratory normal ranges, the local lab data are not used in the statistical analyses. All local laboratory measurements will be listed with the associated reference ranges if available. Abnormal laboratory results of ALT and/or AST $>3 \times$ ULN, TB $>2 \times$ ULN or CK $>5 \times$ ULN based on the non-central laboratory reference ranges (when available) will be noted in the listing.

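### Liver and CK exceedances seen only on local-laboratory results are noted in a listing but do not reach the laboratory-criterion counts or the potential Hy's law plot

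*SAP*

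**What the plan says.** Protocol 10.6.6 states: "Local laboratories may be utilized during the pandemic", at the investigator's discretion. The same provision appears in 10.6.8 (Month 12 and later clinic visits) and 10.6.9 (End of Study).

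SAP 16.3 then sets out how those results are handled:

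- Clinical review: "The local lab data are reviewed and evaluated by the investigators for any abnormalities and adverse event reporting as applicable".
- Analysis: "the local lab data are not used in the statistical analyses". The reasons given are the diversity of units and "variation in laboratory normal ranges".
- Reporting: "All local laboratory measurements will be listed with the associated reference ranges if available".
- Flags: local ALT and/or AST above 3x ULN, total bilirubin above 2x ULN, or CK above 5x ULN, "based on the non-central laboratory reference ranges (when available) will be noted in the listing".

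The outputs that depend on laboratory thresholds are described nearby. SAP 16.1.2 says "AESIs will be identified by specified MedDRA PTs, or the related laboratory criteria if applicable", and SAP 16.3 says "Lab abnormalities associated with AESIs are listed in Appendix 7 and will be summarized with the AESIs". SAP 16.3 also plans shift tables to the worst post-baseline category, by-arm counts of other laboratory abnormalities (Table 3), and a scatterplot for potential Hy's law cases. That plot sets each patient's peak ALT or AST against the concomitant bilirubin, both as multiples of ULN. The laboratory outputs are drawn from the central-laboratory parameter list in Protocol Table 4.

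**The concern.** The plan computes a unit-free flag from local results and then stops at a listing. For a mean or a mean change, pooling laboratories with different units and assays is a real difficulty, and leaving local values out is sensible. For a threshold written as a multiple of ULN, dividing the value by its own laboratory's ULN has already removed the units. The Hy's law plot uses that same scale.

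Hepatic safety (including Hy's law cases) and musculoskeletal safety (including CK) are named AESI categories in Protocol 15.8.1. A patient whose only exceedance was measured locally would be shown in the value-based outputs as not meeting the criterion, or plotted at a lower central peak. What is at stake is the completeness of the absolute counts for uncommon laboratory events. For potential Hy's law cases, it is also whether a reader can see them in one display or must assemble them from separate ALT/AST and bilirubin flags in a listing.

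**Working it through.** The plan gives no figure to reproduce, so the check traces each route by which a local exceedance could reach an output.

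| Output | Source in the plan | Does a local-only exceedance enter? |
|---|---|---|
| By-visit summaries of values and changes | SAP 16.3 | No |
| ALT and AST shift to worst category | SAP 16.3, Table 2 | No |
| Laboratory-criterion AESI counts | SAP 16.1.2, 16.3 (Appendix 7 not available to me) | No, by the exclusion sentence |
| Other laboratory-abnormality counts | SAP 16.3 (Table 3 not available to me) | No, by the exclusion sentence |
| Potential Hy's law plot | SAP 16.3 | No, by the exclusion sentence |
| TEAE tables and AESI counts by preferred term | SAP 16.1.1, 16.1.2 | Yes, if reported as an AE (for AESI, under a listed term) |
| Any laboratory count, through a confirmatory repeat | Protocol 12.1.6.3.1, 12.1.6.3.2 | Yes, if the repeat is central and still exceeds the threshold |
| Local-laboratory listing | SAP 16.3 | Yes; flagged where a range exists |

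**How far the adverse-event route reaches.** Protocol 13.1.3 asks for clinically significant laboratory findings to be reported as AEs, without distinguishing central from local. Protocol 13.2.3 limits this: a value not already tied to an AE is recorded only if it led to action on study drug, required intervention, or was judged clinically significant. An asymptomatic exceedance with none of these need not be recorded. A recorded AE also adds no point to the Hy's law plot.

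**How far the repeat reaches.** Protocol 12.1.6.3.1 (ALT/AST above 3x ULN) and 12.1.6.3.2 (CK above 5x ULN) call for a confirmatory repeat but do not say which laboratory does it. The plot uses the peak value, and a later central repeat may be lower.

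**How much central data there is around a local draw.** After Month 6, scheduled safety laboratory tests are six months apart (Protocol Appendix 1). When a visit became remote, the minimum data set in Protocol 10.6.6, 10.6.8 and 10.6.9 does not include laboratory samples; home-nurse visits are expected to collect central samples where logistically possible. A local draw may therefore be the only result in its interval.

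**Size, in symbols.** Let *s* be the share of patients meeting a criterion who meet it only on a local result, with no central exceedance at any time. Let *a* be the share of those reported as an AE that is counted in a table.

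- Shortfall in the laboratory-criterion count = *s*.
- Shortfall across all tables = *s* x (1 - *a*).

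The documents give neither quantity. On assumed values:

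| *s* (assumed) | Laboratory-criterion count low by | Absent from all tables, *a* = 0 | *a* = 0.5 | *a* = 1 |
|---|---|---|---|---|
| 1% | 1% | 1.0% | 0.5% | 0% |
| 5% | 5% | 5.0% | 2.5% | 0% |
| 10% | 10% | 10.0% | 5.0% | 0% |

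**Effect on the comparison.** If *s* is the same in both arms and the true proportions are p1 and p0, the observed ratio is (1 - *s*)p1 / [(1 - *s*)p0] = p1/p0, which is unchanged. The observed difference is (1 - *s*)(p1 - p0), smaller by the factor (1 - *s*).

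**The case against.** The strongest reply is that the plan already sends local results to the place where they matter clinically. Investigators review them and report AEs, and those AEs are tabulated. For the most serious pattern the protocol goes further. Under 12.1.6.3.1, confirmed ALT/AST above 3x ULN with bilirubin above 2x ULN and no alternative reason leads to stopping study drug, and under 13.2.3 an action on study drug makes the abnormality recordable as an AE. The same holds for the confirmed, unexplained CK elevations that lead to stopping under 12.1.6.3.2. The Hy's law definition in Protocol 15.8.1 also requires no known other cause, a case-level judgement that a flagged listing can support.

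That reply stands against a stronger reading. A reader might infer that local exceedances are missing from every table. The documents do not support this: reported exceedances reach the TEAE and preferred-term AESI tables, and a central repeat that still exceeds the threshold reaches the laboratory counts. The reply does not cover an unreported asymptomatic exceedance, and it does not put any point on the plot.

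Two further objections have weight. First, dividing by ULN removes units but not the variation in normal ranges, because the ULN is the denominator; some ranges will be missing altogether. This argues for keeping central-only results as the main presentation, but not for omitting a supplementary row. Second, exposure is limited: the local-laboratory provision appears from Month 6 onward and not at Month 1 or Month 3 (Protocol 10.6.4, 10.6.5).

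**Conclusion.** The point holds in a narrow form. An exceedance seen only on a local result and not repeated centrally is absent from the laboratory-criterion counts and the potential Hy's law plot. If it is also not reported as an AE, it appears only in the listing. For the flagged criteria the units rationale does not justify stopping at a listing; the variation in normal ranges is a fair reason for caution.

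The size is unknown. A reader might be tempted to multiply a guessed share of local draws by a guessed number of patients with exceedances to get a case count per arm. The documents supply neither rate, and a share of draws is not a share of patients: a patient is missed only if no central draw ever shows the exceedance. A reader might also infer that one uncounted Hy's law case would overturn the safety conclusion. Nothing in the documents shows that; a confirmed case should reach the AE tables, and flagged values remain visible in the listing. Nor is there evident bias between arms. With treatment blinded there is no apparent reason for local testing or reporting to differ by arm, so the expected effect is lower absolute counts and a slightly smaller absolute difference.

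The conclusion rests on reading the exclusion sentence as covering the AESI laboratory criteria and the plot. SAP Appendix 7, Table 3 and Section 17.3 (COVID-19 related safety assessments) were not in the text available to me, and any of them could add handling not seen here. I rate this as a cheap improvement in reporting, below the level of a change the plan should be required to make.

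**What to change.** - Keep the central-only counts as the main presentation.
- Beside them, add a supplementary by-arm count of patients meeting each multiple-of-ULN criterion (ALT/AST above 3x, bilirubin above 2x, CK above 5x) on central or local results, using local value over local ULN where the range is available.
- Show local ALT/AST-bilirubin pairs on the potential Hy's law plot with a distinct symbol.
- Keep local values out of the mean and mean-change summaries, where the units objection is valid.

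The cost is a little programming, since the flags are already to be produced for the listing. The downside is that local ULNs vary and some ranges are missing, so the supplementary count mixes laboratories and is incomplete; the central-only row beside it makes that visible. If Appendix 7, Table 3 or Section 17.3 already provides such a count, a cross-reference in SAP 16.3 would be enough for that part.

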16.4. Electrocardiogram Evaluations

The Investigator's judgment of overall assessment of electrocardiograms (Normal; Abnormal, Not Clinically Significant; or Abnormal, Clinically Significant) will be recorded, and will be summarized at baseline and at the (nominal) end-of-study visits.

16.5. Vital Signs

The following vital signs measurements will be reported for this study:

- Systolic blood pressure (SBP) (mmHg)
- Diastolic blood pressure (DBP) (mmHg)
- Heart rate (HR) (beats per minute [bpm])
- Weight (kg)
- Height (cm) (at screening only)
- BMI (kg/m^2) (calculated)

[figure not shown]
Summaries will be provided for SBP, DBP, and HR for observed values and change from baseline values by visit.

[figure not shown]
Measurement, absolute change from baseline and percent change from baseline of weight will be summarized by baseline glycemic status and by baseline BMI categories.

[figure not shown]
Patients with potentially clinically significant vital sign abnormalities (Appendix 10) will be listed. For a given parameter, all the patients' values will be included in the listing if any value meets the criteria.

[figure not shown]
16.6. Physical Examination

Abnormalities in physical examinations will be presented in a listing.

APPENDIX 1. SCHEDULE OF EVENTS

	Screen and Run-In		Treatment														
							PV		PV		PV		PV		PV		PV
Visit	S1 ¹	S2	T1	T2	T3	T4 ⁸	T5 ⁸	T6 ⁸	T7 ⁸	T8 ⁸	T9 ⁸	T10 ⁸	T11 ⁸	T12 ⁸	T13 ⁸	EOS ^{9,10}	PT1
Week/ Month	Wk -5	Wk -4	Day 1/ Wk 0	Mth 1	Mth 3	Mth 6	Mth 9	Mth 12	Mth 15	Mth 18	Mth 21	Mth 24	Mth 27	Mth 30	Mth 33		
Procedure	Day -35	Day -31 to -25		±3 Days	±5 Days	±5 Days	±10 Days	±10 Days	±10 Days	±10 Days	±10 Days	±10 Days	±10 Days	±10 Days	±10 Days		30 days ±10 after EOS
Informed Consent	X																
Enrollment Criteria	X	X	X														
Demographics	X																
Medical History	X																
Concomitant Medications	X	X	X	X	X	X	X	X	X	X	X	X	X	X	X	X	
Diet and Exercise Counseling	X	X	X	X	X	X	X	X	X	X	X	X	X	X	X	X	
Adverse Event Recording	X	X	X	X	X	X	X	X	X	X	X	X	X	X	X	X	X
Physical Exam		X														X	
Weight ²	X		X	X	X	X		X		X		X		X		X	

	Screen and Run-In		Treatment															
							PV		PV		PV		PV		PV		PV	
Visit	S1 ¹	S2	T1	T2	T3	T4 ⁸	T5 ⁸	T6 ⁸	T7 ⁸	T8 ⁸	T9 ⁸	T10 ⁸	T11 ⁸	T12 ⁸	T13 ⁸	EOS ^{9,10}	PT1	
Week/ Month	Wk -5	Wk -4	Day 1/ Wk 0	Mth 1	Mth 3	Mth 6	Mth 9	Mth 12	Mth 15	Mth 18	Mth 21	Mth 24	Mth 27	Mth 30	Mth 33			30 days ±10 after EOS
Procedure	Day -35	Day -31 to -25		±3 Days	±5 Days	±5 Days	±10 Days	±10 Days	±10 Days	±10 Days	±10 Days	±10 Days	±10 Days	±10 Days	±10 Days			
Height	X																	
12-Lead ECG		X															X	
Vital Signs ³	X		X	X	X	X		X		X		X		X		X		
Serology ⁴		X																
Serum or Urine Pregnancy/ FSH ⁵	X		X															
TSH	X																	
Clinical Safety Labs ⁶	X		X	X	X	X		X		X		X		X		X		
Basic Fasting Lipids ⁷	X	X	X		X	X		X		X		X		X		X		
HbA _{1c}	X				X	X		X		X		X		X		X		
hs-CRP			X			X		X									X	
Randomization			X															
Single-Blind Drug Dispensing		X																

	Screen and Run-In		Treatment														
							PV		PV		PV		PV		PV		
Visit	S1 ¹	S2	T1	T2	T3	T4 ⁸	T5 ⁸	T6 ⁸	T7 ⁸	T8 ⁸	T9 ⁸	T10 ⁸	T11 ⁸	T12 ⁸	T13 ⁸	EOS ^{9,10}	PT1
Week/ Month	Wk -5	Wk -4	Day 1/ Wk 0	Mth 1	Mth 3	Mth 6	Mth 9	Mth 12	Mth 15	Mth 18	Mth 21	Mth 24	Mth 27	Mth 30	Mth 33		30 days ±10 after EOS
Procedure	Day -35	Day -31 to -25		±3 Days	±5 Days	±5 Days	±10 Days	±10 Days	±10 Days	±10 Days	±10 Days	±10 Days	±10 Days	±10 Days	±10 Days		
Single-Blind Drug Return			X														
Double-blind Drug Dispensing			X		X	X		X		X		X		X			
Double-Blind Drug Return					X	X		X		X		X		X		X	

ALT = alanine aminotransferase; AST = aspartate aminotransferase; CK = creatine kinase; DBP = diastolic blood pressure; ECG = electrocardiogram; eGFR = estimated glomerular filtration rate; EOS = End of Study; FSH = follicle-stimulating hormone; HbA_{1c} = glycated hemoglobin; HBsAg = hepatitis B surface antigen; HCV-Ab = hepatitis C antibody; HDL-C = high-density lipoprotein cholesterol; HR = heart rate; hs-CRP = high-sensitivity C-reactive protein; Labs = laboratory tests; LDL-C = low-density lipoprotein cholesterol; MACE = major adverse cardiovascular event; SBP = systolic blood pressure; TC = total cholesterol; TG(s) = triglyceride(s); TSH = thyroid-stimulating hormone; PV=phone visit; wk=weeks; mth=month.

¹ An additional visit approximately 1 week after Visit S1 and prior to Visit S2 MAY be completed if patient’s LDL-C and/or TG level fails to meet entry criteria. Also, an additional visit and/or assessment between Visits S1 and T1 MAY be completed if the patient’s DBP, SBP, TSH, eGFR, ALT, AST, and/or CK fails to meet entry criteria. If this optional visit/assessment is completed, the value from the repeat visit/assessment will be used to determine eligibility. Also, at Visit S1 an optional hs-CRP may be measured only if needed for Reynolds Risk Score and a local hs-CRP value is not available. Finally, the number of days between Week -5 (Visit S1) and Week -4 (Visit S2) may be less than 7, and the number of days between Week -5 (Visit S1) and randomization may be less than 35 as long as eligibility can be determined.

² Body weight will be measured in the morning while fasting, using consistent scales, after voiding, and without shoes and outerwear (eg, coats).

³ Vital signs will include DBP, SBP, HR and will be collected prior to any blood sample collection. The patient will rest for several minutes prior to assessments.

⁴ Serology for HBsAg and HCV-Ab.

⁵ Pregnancy tests completed in premenopausal women only, serum test at Week -5 (Visit S1) and urine test at Day 1 (Visit T1); FSH completed on postmenopausal women <55 years of age.

	Screen and Run-In		Treatment															
							PV		PV		PV		PV		PV		PV	
Visit	S1 ¹	S2	T1	T2	T3	T4 ⁸	T5 ⁸	T6 ⁸	T7 ⁸	T8 ⁸	T9 ⁸	T10 ⁸	T11 ⁸	T12 ⁸	T13 ⁸	EOS ^{9,10}	PT1	
Week/ Month	Wk -5	Wk -4	Day 1/ Wk 0	Mth 1	Mth 3	Mth 6	Mth 9	Mth 12	Mth 15	Mth 18	Mth 21	Mth 24	Mth 27	Mth 30	Mth 33			
Procedure	Day -35	Day -31 to -25		±3 Days	±5 Days	±5 Days	±10 Days	±10 Days	±10 Days	±10 Days	±10 Days	±10 Days	±10 Days	±10 Days	±10 Days	±10 Days	±10 Days	30 days ±10 after EOS

[figure not shown]
⁶ Clinical safety laboratory tests include hematology, blood chemistry, and urinalysis. Urinalysis includes dipstick measured at the clinic and microscopic, if abnormal, completed by the central lab. A limited safety laboratory assessment (ALT, AST, TB, and CK) will be completed at Visit T2 only. A coagulation panel will be completed only if needed for patients on anticoagulant therapy at Day 1 (Visit T1) and 3 to 5 days later.

⁷ Basic fasting lipids include TC, calculated LDL-C, HDL-C, non-HDL-C, and TGs.

⁸ After Visit T4 (Month 6), telephone and clinic visits (alternating every 3 months) will continue until the study is completed.

⁹ All procedures will be completed at the EOS or Early Termination Visit.

¹⁰ Duration of treatment for each patient will vary and is dependent on accumulation of MACE in the entire study. For individual patients, treatment duration will be a minimum of 24 months and may continue for up to approximately 57.5 months.

